 513 (because of unforeseen circumstances) are unable or unwilling to return for all follow-up visits
 514 will be permitted to return for key visits only as an alternative to withdrawal from the study.
 515 Participants who are not using a device during the post-outcome phase but have not received
 516 alternative treatment will be given the option to continue study visits or end study participation
 517 early.

518

519 Additional phone contacts may be performed as needed.

520 **3.2.1 Text Message Reminders**

521 For participants randomly assigned to text message reminders, periodic messages will be sent by
 522 the Coordinating Center with a reminder to comply with the study device schedule.

523 **3.3 Procedures at Study Visits**

524 The following procedures will be performed in both groups at each visit, unless otherwise
 525 specified:

- 526 1. E-ETDRS visual acuity testing (best corrected) in each eye.
 - 527 • A protocol refraction in the study eye is required at each visit. Refraction in the non-study
 528 eye is only required at the 4 and 8 month visits. When a refraction is not performed, the
 529 most recently performed refraction is used for the testing.
- 530 2. Spectral-Domain OCT using Zeiss Cirrus or Heidelberg Spectralis in both eyes
 - 531 • The same machine type (Cirrus or Spectralis) used at baseline should be used during
 532 follow-up.
- 533 3. Ocular exam in the study eye, including slit lamp examination with lens assessment,
 534 measurement of intraocular pressure, and dilated ophthalmoscopy.
 - 535 • Required at Primary Outcome and 4-Month Post Outcome visits only. Otherwise,
 536 ocular exam is at investigator discretion. In general, an ocular exam should be
 537 completed if the OCT and/or visual acuity have worsened since baseline (e.g. more
 538 than 10% increase in CSF thickness or 5 letter loss in VA).

539 4. OCT angiography on the study eye if obtained at baseline (4 month/primary outcome visit
540 only)

- 541 • Only obtained by a subset of sites with OCT angiography capabilities.
- 542 • *See procedure manual for more details on acquisition, including which fields to collect*
543 *on a given OCT angiography system.*

544 5. Compliance assessment

- 545 • The site personnel will download the compliance data and re-emphasize the importance
546 of compliance with device use

547 All of the testing procedures do not need to be performed on the same day, provided that they are

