833 A test of superiority will be used in evaluating the following hypotheses for the primary outcome:

834 Null Hypothesis (H_0): There is no difference in the mean change in CST from baseline to 4 months
835 between photobiomodulation (PBM) and sham groups.

836 Alternative Hypothesis (H_a): There is a difference in the mean change in CST from baseline to 4
837 months between PBM and sham groups.

838 Similar hypothesis tests will be conducted for all secondary, exploratory, and safety outcomes.

839 **7.3 Sample Size**

840 **7.3.1 Outcome Projections:**

841 To estimate the standard deviation (SD) of change in OCT CST, data from the DRCR Retina
842 Network Protocol A (Treatment for Central-Involved Diabetic Macular Edema in Eyes with Very
843 Good Visual Acuity) was used. The Protocol A cohort of eyes with 20/25 baseline visual acuity
844 and central subfield thickening treated with modified-ETDRS laser was used for the estimation.
845 In protocol A, 42 eyes in the modified-ETDRS laser group completed a visit within 4 months of
846 randomization. The SD of change in CST adjusted for baseline CST in these eyes was 50 microns
847 (personal communication, [name]). The mean change in CST was -2 microns.

848 The expected change and standard deviation of CST in an untreated group is unknown at this time.

849 **7.3.2 Sample Size Estimates**

850 Table 1 shows total sample size estimates under several scenarios. These calculations assume a
851 Type I error rate of 5%, 90% power, and a two-sided test of superiority (see Section 7.6) with a
852 null hypothesis of no difference between the groups (see Section 7.2).

853

854 **Table 1: Total Sample Size Under Various Assumptions for True Mean Change and**
 855 **Standard Deviation**

Mean Treatment Group Difference, microns	Change in Central Subfield Standard Deviation, microns (adjusted for baseline)			
	40	50	60	70
20	172	266	382	518
30	78	120	172	232
40	46	68	98	132

856 Assuming an effective standard deviation of 50 microns and a true difference in mean CST of 30
 857 microns, the required total sample size is 120 eyes to achieve 90% power. Sample size will be
 858 increased to 134 eyes to account for 10% lost to follow-up.

859 **7.4 Outcome Measures Phase 1 (Baseline to completion of the 4-Month/Primary outcome**
 860 **visit)**

861 *Primary Efficacy Endpoint(s)*: Mean change in CST from baseline

862 *Secondary Efficacy Endpoint(s)*:

- 863 • Mean change in retinal volume from baseline

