19 Study eyes will be assigned randomly to the two treatment groups in a 1:1 ratio stratified by site
20 and recent (within 4 months) or planned intravitreous treatment in the non-study eye, including
21 intravitreous anti-VEGF and steroid. Participants may have only one study eye enrolled in the
22 randomized trial.

23 **2.0 Efficacy Analysis Plan**

24 **2.1 Primary Outcome Analysis**

25 The primary analysis will consist of a treatment group comparison of mean change in CST from
26 baseline to the primary outcome visit using analysis of covariance, with adjustment for baseline
27 CST and the randomization stratification factor of recent or planned intravitreous treatment in
28 the non-study eye. Given that OCTs can be obtained from either Spectralis or Cirrus images, and
29 that values from these machines cannot be used interchangeably, OCT values will be converted
30 to a common value for reporting and analyses.

31 The primary analysis is an intention-to-treat analysis. All randomized eyes will be included in
32 the primary analysis irrespective of treatment received and will be analyzed according to
33 treatment group assignment at randomization.

34 For the primary analysis, study participants who complete the primary outcome visit without
35 missing data at the primary outcome visit will be considered as the **completer cohort**. Markov
36 chain Monte Carlo (MCMC) multiple imputation with 100 imputations will be used to handle
37 missing data for participants who do not complete the primary outcome visit, i.e., **non-**
38 **completer cohort**. The imputation model will be stratified by treatment group and will include

39 the CST measured at baseline and at all monthly interim visits up to the primary outcome visit
40 along with the randomization stratification factor of recent or planned intravitreous treatment in
41 the non-study eye.

42 For eyes that receive alternative treatment for DME (detailed in Protocol Section 3.6) in Phase 1,
43 data measured after the initiation of the alternative treatment will be considered to be missing
44 before entering the multiple imputation (MI) process, regardless of whether the treatment
45 initiation is per-protocol, and whether the participant completes the primary outcome visit. Then
46 after multiple imputation, the last OCT measurement prior to the initial alternative treatment
47 (LOCF data) will overwrite the MCMC imputed values for all post-treatment visits and will be

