172 **2.1.6 Planned Interim Analyses**

173 There is no formal interim analysis planned for this study. The Data and Safety Monitoring
174 Committee (DSMC) will review tabulated safety and outcome data approximately every 6
175 months while the study is ongoing.

176 **2.2 Secondary Outcome Analyses**

177 Secondary outcome analyses for Phase 1 are summarized in Table 2. The ITT analysis cohort
178 will be used for all secondary outcomes unless otherwise specified. Similar to the primary
179 analysis, eyes that receive alternative treatment for DME (see Protocol Section 3.6) will be
180 considered missing before entering the multiple imputation, and will have the last measurement
181 prior to treatment overwritten the imputed values and will be used for the secondary analysis
182 unless otherwise specified (“MI then LOCF”). Unless otherwise specified, missing data will be
183 imputed with multiple imputation. The imputation model for handling missing data will be
184 stratified by treatment group and include the baseline value of the outcome, the randomization
185 stratification factor, and change in the outcome for the available time points.

186 To ensure that statistical outliers do not have undue impact on analyses of continuous outcomes,
187 change in continuous outcomes from baseline will be truncated to ± 3 standard deviations based
188 on the overall mean and standard deviation at the primary outcome visit from both treatment
189 groups combined. Similar to the primary analysis, the truncation will be applied after multiple
190 imputation and LOCF, and the cutoff values will be calculated from the completers’ data. Binary
191 outcomes will be created from the corresponding continuous outcome measurements, after
192 multiple imputation, LOCF and data truncation.

Table 2. Secondary Outcome Analyses Phase 1 (Baseline to 4 Months).

| Outcome | Analysis Technique |
|---|-----------------------------|
| Mean change in retinal volume from baseline | Analysis of Covariance |
| Percentage of eyes with CST below OCT machine and gender-specific threshold for DME | Logistic regression |
| Percentage of eyes receiving alternative treatment for DME | Descriptive statistics only |
| Percentage of eyes with a 5-letter loss in visual acuity from baseline | Logistic regression |
| Mean change in visual acuity from baseline | Analysis of Covariance |
| Patient compliance | Descriptive statistics only |

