194 Change in retinal volume from baseline is a continuous variable and will be analyzed using
 195 analysis of covariance. The analysis will include adjustment for baseline CST, baseline retinal
 196 volume, and the randomization stratification factor. The estimated treatment-group difference,
 197 95% confidence interval and 2-sided *P* value will be presented. The assumptions of linearity,
 198 normality, and homoscedasticity will be verified using graphical methods. Serious violations
 199 may be addressed by transformation of dependent and/or independent variables, non-parametric
 200 methods, categorizing continuous covariates, and/or excluding covariates.

201 The percentage of eyes with CST below OCT machine and gender-specific threshold for DME at
 202 the primary outcome visit is a binary variable that will be analyzed with logistic regression with
 203 robust variance estimation. LOCF will be used for eyes receiving alternative DME treatment, but
 204 multiple imputation will not be performed for missing data given the thresholds are machine
 205 specific. Baseline CST and the randomization stratification factor will be included as covariates.
 206 The odds ratio for the treatment group effect, 95% confidence interval, and *P* value will be
 207 presented. In addition, the treatment-group risk difference will be computed as the marginal
 208 probabilities from a counterfactual model, and the 95% confidence interval will be estimated
 209 using bootstrap resampling.

210 The percentage of eyes receiving an alternative treatment for DME before the primary outcome
 211 visit will be reported. Only participants receiving alternative treatment or completing the primary
 212 outcome visit without receiving alternative treatment will be included, although it is recognized
 213 that the percentage with alternative treatment will likely be overestimated with this procedure.
 214 Statistical comparison between treatment groups will not be performed.

215 The percentages of eyes with ≥ 5 -letter decrease from randomization at the primary outcome visit
 216 is a binary variable that will be calculated from the continuous visual acuity letter scores and will
 217 be compared between treatment groups using logistic regression with robust variance estimation.
 218 Baseline visual acuity and randomization stratification factor will be included as covariates. The

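### Machine-specific thresholds do not prevent multiple imputation of the CST-below-threshold outcome, so the SAP's stated reason for exempting it does not hold

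*SAP*

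**What the plan says.** SAP 2.2 sets a general rule that binary "outcomes will be created from the corresponding continuous outcome measurements, after" multiple imputation (MI), LOCF and truncation. Later in the same section it makes an exception for the percentage of eyes with CST below threshold. LOCF is kept for eyes given alternative DME treatment, but "multiple imputation will not be performed for missing data given the thresholds are machine" specific. The outcome is tested by logistic regression adjusted for baseline CST and the stratification factor, with an odds ratio, confidence interval and P value. A marginal risk difference with a bootstrap interval is added.

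Three other places bear on the reason given:

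- SAP 2.1 says of Spectralis and Cirrus images "that values from these machines cannot be used interchangeably, OCT values will be converted" to a common value. The primary analysis then imputes CST 100 times by arm, using baseline and interim CST.
- Protocol 3.3 says "The same machine type (Cirrus or Spectralis) used at baseline should be used during" follow-up.
- Protocol 7.8 imputes missing secondary outcomes by default and states no exception when it describes this outcome.

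The other tested binary outcome, loss of 5 or more letters, is derived from imputed visual acuity for its odds ratio. Its bootstrap risk difference uses complete cases with LOCF (SAP 2.2).

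**The concern.** An eye's threshold depends only on its machine and its sex. Both are known even when the month-4 scan is missing, so the stated reason describes a conversion step and not an obstacle. The exception also sits awkwardly beside the general rule a few lines above it, and beside Protocol 7.8.

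What is at stake is modest but real. SAP 8.6 wants this outcome to help interpret the primary result. As planned, it would rest on fewer eyes and a stricter missing-data assumption than the primary analysis, because it ignores the interim CST values that the imputation model uses. The sensitivity analyses in SAP Table 1 and the tipping-point analysis address only the primary outcome, so nothing planned would show whether the exemption matters.

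**Working it through.** **1. The plan's own figures.** Inputs from Protocol 7.3.2: two-sided alpha 0.05, power 90%, SD 50 microns, difference 30 microns, 1:1 allocation.

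- Normal formula: n per arm = 2 × (1.960 + 1.282)² × 50² / 30² = 2 × 10.51 × 2.778 = 58.4, so 59 per arm or 118 in total.
- With the t distribution, 60 per arm gives 90.3% power, so 120 in total. This matches the protocol.
- 120 / 0.90 = 133.3, rounded up to 134. This matches "increased to 134 eyes to account for 10% lost to follow-up".

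The documents give no response rate or power for the threshold outcome.

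**2. Eyes lost.** 134 × 0.10 = 13.4, so about 13 eyes leave and about 120 remain. This is a ceiling at the planned loss, because any non-completer who had alternative DME treatment stays in through LOCF.

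**3. Is imputation possible?** For a missing eye, in each imputed dataset, the outcome is 1 if imputed CST is below T(machine, sex), with both on the same scale.

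| Needed | Available from |
|---|---|
| Sex | Protocol 2.3.2, baseline demographics |
| Machine | Baseline OCT (Protocol 2.3.2), same type intended in follow-up (Protocol 3.3) |
| Imputed CST | SAP 2.1, 100 datasets, after conversion to a common scale |
| Threshold | Assumed to be the eligibility values in Protocol 2.2.2: Cirrus 290 (women) and 305 (men); Spectralis 305 and 320 |

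The two machines' thresholds differ by 305 − 290 = 15 microns in women and 320 − 305 = 15 in men. The conversion formula is not in the documents, but the primary analysis already depends on it. With any increasing conversion, it makes no difference whether the threshold is converted or the CST value is back-converted.

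**4. Possible bias.** Missingness and response rates are not in the documents, so the results below rest on assumptions. All scenarios are missing at random given interim CST. Figures are the PBM-minus-sham difference in percentage points.

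| Dropout assumption | Full data or truth | Complete-case | MI then threshold |
|---|---|---|---|
| Same link to month-3 CST change in both arms, 30-micron effect | 19.8 | 19.5 | 19.8 |
| Linked to worsening in sham only (about 6% missing PBM, 11% sham) | 13.9 | 12.1 | 13.8 |
| Opposite directions by arm, no effect | 0.2 | 5.2 | 0.4 |
| Opposite directions by arm, 30-micron effect | 19.8 | 24.5 | 19.9 |

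Rows 1, 3 and 4 use 134 eyes, SD of change 50 at month 4, correlation 0.8 between adjacent visits, about 8–10% missing, an unadjusted risk difference and 400 replicates (Monte Carlo error about 0.4 points). In rows 3 and 4, PBM eyes tend to leave when thickening and sham eyes when thinning. Row 2 uses 67 per arm, 300 trials and imputation from baseline and month-3 CST.

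The shifts are 19.5 − 19.8 = −0.3, 12.1 − 13.9 = −1.8, 5.2 − 0.2 = +5.0 and 24.5 − 19.8 = +4.7.

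A version closer to the planned model (logistic regression adjusted for baseline CST, standardised risk difference, 800 trials) gave about 1.7 points against PBM for sham-only dropout (6% vs 10% missing), and 0.3 or less when both arms shared one mechanism. The per-trial standard error was about 8 points.

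**5. Precision.** Nominal power for assumed rates in sham and PBM:

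| Rates | 60 per arm | 67 per arm |
|---|---|---|
| 10% vs 20% | 33% | 37% |
| 20% vs 40% | 67% | 72% |
| 30% vs 50% | 61% | 66% |

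The gain is at most about 5 points. The 67-per-arm column is an upper limit for MI, which does not restore full information.

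**The case against.** A reader might infer that dropping these eyes breaches the intention-to-treat rule. It does not. SAP 8.1 and SAP 2.2 both allow stated exceptions, SAP 8.3 leaves missing-data handling to each analysis, and eyes are still analysed as randomized.

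A reader might also infer that the comparison will be biased. The documents do not support that either. Participants are masked until the 4-month visit, nothing suggests that dropout would follow interim CST differently by arm, and one shared mechanism gives almost no bias. The adjusted logistic model is valid if missingness depends only on treatment, baseline CST and stratum. Even in the sham-only scenario the shift is about 2 points against a standard error of about 8.

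Other points on that side also stand:

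- Complete-case with LOCF is already used in this SAP for the 5-letter risk difference.
- Sensitivity Analysis #1 runs the primary CST outcome on essentially the same eyes, so the two can be read together.
- Pooling a bootstrap risk difference over imputations needs a method that the SAP does not set out.
- Protocol 3.3 says only that the same machine should be used, so a switch is possible. An eye with no scan can still be assigned its baseline machine.

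These points limit the size of the issue and shape the fix. None of them shows that a machine-specific threshold prevents imputation.

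**Conclusion.** The reason given for the exemption does not hold, and the exception should be reconciled with the general rule in SAP 2.2 and the default in Protocol 7.8. The loss is at most about 13 of 134 eyes at the planned 10%. Bias is possible but not established: near 0 to about 2 points in the milder scenarios and about 5 in a deliberately extreme one, with a direction that depends on the dropout pattern. These figures rest on assumed dropout, correlation and response rates. MI matched the full data in the tabulated scenarios because they satisfy missing at random, which the SAP already assumes for the primary analysis.

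The outcome is supportive under SAP 8.6, and the trial is a pilot. The primary conclusion is unaffected. This is a cheap improvement.

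**What to change.** Replace the exemption in SAP 2.2 with the following:

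- Take the imputed CST datasets from the primary analysis. After MI and LOCF, in the order that the SAP's general rule sets, compare each eye's CST with the threshold for its sex and machine. Use the baseline machine where the scan is missing. Either convert the threshold to the common scale or back-convert the CST value, and state which.
- Fit the planned logistic model with robust variance in each dataset and pool the log odds ratio by Rubin's rules.
- Keep complete-case with LOCF as a sensitivity analysis for the odds ratio, and as the basis of the bootstrap risk difference, as the SAP already does for 5-letter loss.

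The cost is some extra programming, plus reliance on the OCT conversion that the primary analysis already uses. No new data or imputations are needed. If the exemption is kept instead, give a reason that holds, state the missing-data assumption, and align the two statements in SAP 2.2 with Protocol 7.8.

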439 *within 3 weeks after randomization.*

440 **2.4 Randomization of Eligible Subjects**

441 1. Prior to randomization, the study participant's understanding of the trial, compliance with
442 device use, willingness to accept the assigned treatment group, and commitment to the follow-
443 up schedule will be reconfirmed.
444
445 2. Randomization is completed on the DRCR.net website.
446 • Study participants will be assigned randomly (stratified by site and intravitreous treatment*
447 in the non-study eye) with equal probability to one of two treatment groups:
448 ○ Active treatment (670nm wavelength) device
449 ○ Sham (broad spectrum white light) device
450

451 *Randomization will be stratified by site and recent (within 4 months) or planned intravitreous
452 treatment in the non-study eye, including intravitreous anti-VEGF and steroid
453

454 3. For participants who consent, a second randomization will determine whether the participant
455 will receive periodic text message reminders regarding device compliance.
456 • Randomization is completed on the DRCR.net website and will be stratified by assigned
457 treatment group.

458
459 Once a study participant is randomized, that participant will be counted regardless of whether the
460 assigned treatment is received. Thus, the investigator must not proceed to randomize an individual
461 until he/she is convinced that the individual is eligible and will accept whichever treatment group
462 is assigned through randomization.
463

464 **CHAPTER 3: RANDOMIZED TRIAL PROCEDURES**

465 **3.1 Study Device**

466 **3.1.1 Home Procedures**

467 While a device is assigned, the study participant will be required to use the device twice daily
468 (once in the morning and once before bed) for 90 seconds each. Participants will be provided with
469 instructions to take home for proper device use and the required timing of treatments.

470

471 **3.1.2 Primary Outcome Phase**

472 Each participant will receive the type of device for home use based on their treatment group
473 assignment (the participant will remain masked to whether the device is emitting active or sham
474 treatment):

475 ○ Active treatment (670nm wavelength) device twice a day for 90 seconds
476 ○ Sham (broad spectrum white light) device twice a day for 90 seconds

477

478 The primary outcome phase will last until completion of the '4-month' visit, which could be up to

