479 8 months post-randomization (see visit windows below). If the visit is not completed by 8 months,
480 the participant will be instructed to discontinue device use, return the study device as soon as they
481 are able, and study participation will be ended.

482

483 **3.1.3 Post-Outcome Phase**

484 At the 4-month visit, all participants will be unmasked to their treatment group assignment.

485

486 Participants originally assigned to Sham who have not already received alternative DME treatment
487 (see section 3.6) will return the original device and have the option to receive the active treatment
488 group device for the next 4 months.

489

490 Participants originally assigned to Active who have not received alternative treatment will return
491 the original device and have the option to complete the remaining follow-up visits without device
492 use.

493

494 **3.1.4 Device Training**

495 On the day of randomization, a device will be provided to the participant according to their
496 randomized assignment. In order for investigators to remain masked, clinical site coordinators
497 will instruct study participants regarding the proper use of the device. The eyelid must be closed
498 for the duration of the treatment. The participant must turn the device on and it will stop
499 automatically. The study participant will be asked to demonstrate proper use in the office, which
500 will be considered the initial treatment. The participant will be instructed to complete the second
501 treatment that day before bed.

502

503 **3.2 Study Visits and Phone Contacts**

504 A phone call is completed by site personnel within approximately one week of randomization (5
505 to 14 days) to emphasize compliance with device use and answer any questions.

506

507 Scheduled follow-up visits will occur at the following times (time from randomization unless
508 otherwise noted):

509

Visit	Target Date	Target Window (around Target Date)	Allowable Window (around Target Date)
1 Month	4 weeks	± 1 week	± 2 weeks
2 Month	8 weeks	± 1 week	± 2 weeks
3 Month	12 weeks	± 1 week	± 2 weeks
4 Month/Primary Outcome Visit*	16 weeks	± 2 weeks	-4 weeks/+16 weeks
~6 Month/2-month post outcome	8 weeks after 4- Month visit	± 2 weeks	± 4 weeks
~8 Month/4-month post outcome	16 weeks after 4- Month visit	± 2 weeks	-8 weeks/+12 weeks

510

*Key visit

511

512 The goal will be for all participants to complete all scheduled visits. However, participants who

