948 robust variance estimation. Baseline CST and the randomization stratification factor will be
949 included as covariates.

950 The percentage of eyes receiving an alternative treatment for DME before the primary outcome
951 visit will be reported. Only participants receiving alternative treatment or completing the primary
952 outcome visit without receiving alternative treatment will be included. Statistical comparison
953 between treatment groups will not be performed.

954 The percentages of eyes with 5-or-more-letter decrease from randomization at primary outcome
955 visit is a binary variable that will be compared between treatment groups using logistic regression
956 with robust variance estimation. Baseline visual acuity and randomization stratification factor will
957 be included as covariates. The mean change in visual acuity will also be reported; however,
958 statistical comparison between treatment groups for the mean change will not be performed.

959 For each logistic regression analysis, the odds ratio for the treatment group effect, 95% confidence
960 interval, and P value will be presented.

961 **7.9 Safety Analyses**

962 All reportable adverse events will be categorized as study eye or systemic. All events will be
963 tabulated by treatment group in a listing of each reported Medical Dictionary for Regulatory
964 Activities (MedDRA) term and summarized over each MedDRA System Organ Class. All
965 randomized participants will be included in safety analyses.

966 Since there are no known risks of the device, there are no pre-specified safety outcomes of interest.
967 However, the frequency of each ocular adverse event occurring at least once per eye and each
968 systemic event occurring at least once per participant will be calculated.

969 In addition, the following will be tabulated by treatment group:

970 • For each MedDRA System Organ Class, percentage of participants with at least one
971 serious event
972 • Number of adverse events thought by investigator to be related to treatment

973 No formal statistical comparisons will be performed for reported adverse events.

974 **7.10 Outcome Measures Phase 2 (4 Months Post-Outcome)**

975 The following post-switch effects on DME from completion of the 4-month/primary outcome visit
976 to the final visit will be tabulated separately within each treatment group:

977 • Duration of effect on DME after active treatment is stopped

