390 angiography. The statistical analysis plan will be detailed in a separate document.

391 **8.0 General Principles for Analysis**

392 **8.1 Analysis Cohort**

393 Unless otherwise stated, all treatment comparison analyses will follow the intention-to-treat
394 principle with all randomized eyes included and each eye analyzed according to the randomized
395 treatment assignment, regardless of treatment actually received.

396 **8.2 Visit Windows for Analysis**

397 For common visits, the analysis windows will be defined according to Table 3. For visits falling
398 in more than 1 window, priority will be given to the key outcome visits. Otherwise, the visit will
399 be assigned to the earlier window (e.g., a visit on day 42 would be assigned as the 1-month visit).

400 **Table 3. Analysis Windows for Outcome Visits**

| Visit (Protocol Window) | Target | Analysis Window | |
|---|---------------------------------|-----------------|-----------------|
| 1 Month (± 1 week) | 4 weeks | 14 – 42 days | (2 – 6 weeks) |
| 2 Month (± 1 week) | 8 weeks | 42 – 70 days | (6 – 10 weeks) |
| 3 Month (± 1 week) | 12 weeks | 70 – 98 days | (10 – 14 weeks) |
| 4 Month/Primary Outcome * (± 2 week) | 16 weeks | 84 – 224 days | (12 – 32 weeks) |
| ~6 Month/2-Month Post Outcome (± 2 week) | 8 weeks after 4-Month visit | 140 – 280 days | (20 – 40 weeks) |
| ~8 Month/4-Month Post Outcome* (± 2 week) | 16 weeks after 4-Month visit | 168 – 336 days | (24 – 48 weeks) |

401 *Key visits

402 **8.3 Missing Data**

403 The strategy for handling missing data generally is included with the description of each
404 individual analysis. Where not otherwise specified, only participants with non-missing data are
405 included in the analysis.

406 **8.4 Outliers**

407 To help ensure that statistical outliers do not have undue impact on analyses of continuous
408 outcomes including visual acuity, OCT central subfield thickness (primary outcome) and retinal
409 volume, change in continuous outcomes will be truncated to ± 3 standard deviations based on the
410 overall mean and standard deviation at the primary outcome visit for primary outcome
411 completers' data, irrespective of treatment group. Visual acuity letter score, change in visual
412 acuity from baseline, OCT central subfield thickness, change in CST from baseline, and change
413 in retinal volume from baseline will be truncated. Truncation will be performed after imputation

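### The percentage of eyes given alternative DME treatment drops untreated non-completers and counts to a visit at 12 to 32 weeks; a fixed-time Kaplan-Meier estimate beside it would cost almost nothing

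*SAP*

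**What the plan says.** The Protocol Summary lists this percentage among the key secondary efficacy outcomes. SAP 2.2 defines it as "The percentage of eyes receiving an alternative treatment for DME before the primary outcome" visit and restricts the denominator: "Only participants receiving alternative treatment or completing the primary" outcome visit without such treatment are counted. It then recognizes "that the percentage with alternative treatment will likely be overestimated with this procedure". Protocol 7.8 has the same restriction ("visit will be reported. Only participants receiving alternative treatment or completing the primary" outcome visit untreated) without that remark.

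The outcome is descriptive. SAP 2.2 says "Statistical comparison between treatment groups will not be performed", and Protocol 7.4 and SAP Table 2 agree.

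The end of counting is a visit, not a fixed time. Protocol 3.2 sets its target at 16 weeks, with a target window of 2 weeks either side and an allowable window of minus "4 weeks/+16 weeks", that is, weeks 12 to 32. SAP Table 3 uses the same range, 84 to 224 days. Protocol 3.1.2 adds: "The primary outcome phase will last until completion of the '4-month' visit, which could be up to" 8 months after randomization. SAP Table 2 nevertheless labels the Phase 1 outcomes as baseline to 4 months. Neither document gives a fixed time point, a censoring rule or a time-to-event estimate for this outcome.

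**The concern.** An eye treated and then lost stays in the calculation, while an eye lost untreated leaves it. That pushes the percentage up, and further up in the arm with more loss. Separately, the proportion ever treated can only grow with time, so an arm or a trial with later visits shows a higher percentage at the same underlying risk. A reader of Table 2 would take the figure as a 4-month risk.

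Late visits are plausible: the SAP revision history records an 8-week extension of this window as a COVID-19 response. Timing is handled elsewhere. Protocol 7.6 plans a CST sensitivity analysis limited to 4 weeks before and 8 weeks after target, and SAP 4.0 adjusts the compliance analyses for days since randomization. This outcome has no such handling. At stake is how accurately one descriptive secondary outcome is reported, in a table where readers will compare arms by eye.

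**Working it through.** **Inputs.** Loss of 10%, 134 eyes, 1:1 allocation (Protocol 7.3.2 and Summary). The stated total reproduces: 120/0.90 = 133.3, taken up to 134, or 67 per arm, of whom about 7 are lost. The plan states no alternative-treatment rate, so there is no figure of its own to reproduce. The only benchmark is the trigger for SAP Sensitivity Analysis #5, 6 eyes (10%) in either group. Assumption: 16-week risk F of 5% to 20%.

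**1. Counts in one arm of 67 with 7 untreated losses.**

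| Treated eyes | Planned (n/60) | All randomized (n/67) |
|---|---|---|
| 3 | 5.0% | 4.5% |
| 6 | 10.0% | 9.0% |
| 10 | 16.7% | 14.9% |

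The first column ignores the untreated time of the lost eyes. The second assumes that no lost eye would have been treated. One is too high and the other too low.

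**2. Size of the denominator bias, visits on target.** Let λ = −ln(1−F)/16 and δ = −ln(1−L)/16, with L the loss by week 16. For a visit at week V, treated E = λ/(λ+δ) × [1 − exp(−(λ+δ)V)], untreated completers C = exp(−(λ+δ)V), and planned percentage = E/(E+C). With V = 16 and L = 10%:
- F = 5%: 0.0475/(0.0475 + 0.855) = 5.3%
- F = 10%: 0.095/(0.095 + 0.81) = 10.5%
- F = 20%: 0.190/(0.190 + 0.72) = 20.9%

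The excess is 0.3, 0.5 and 0.9 points. At F = 10%, a loss of 20% gives 11.1%, so arms losing 10% and 20% would differ by 0.6 points with equal true risk. The standard error per arm, √(F(1−F)/67), is 2.7, 3.7 and 4.9 points.

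**3. Timing, if risk accrues at a constant rate.** A 10% risk at 16 weeks is 1 − 0.9^(12/16) = 7.6% at 12 weeks and 1 − 0.9^(32/16) = 19.0% at 32 weeks. Those are the extremes. Averaging E and C from step 2 over assumed visit patterns (F = L = 10%):

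| Primary visits | E | C | Planned % |
|---|---|---|---|
| Evenly over weeks 14–18 | 9.50% | 81.01% | 10.5 |
| 70% weeks 14–18, 30% weeks 18–32 | 10.84% | 78.32% | 12.2 |
| Evenly over weeks 12–32 | 12.47% | 75.06% | 14.2 |

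Against the first row, late visits add 1.7 and 3.7 points. In a simulation of 400,000 eyes with random loss, Kaplan-Meier at week 16 returned 10.0% under all three patterns.

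**4. Timing, if treatment starts only at the interim visits (weeks 4, 8, 12).** With total risk 10%, the risk per visit is p = 1 − 0.9^(1/3) = 0.0345. Then E = p·0.9^(4/16) + p(1−p)·0.9^(8/16) + p(1−p)²·0.9^(12/16) = 0.0949, and C = 0.9 × the mean of 0.9^(V/16). C is 0.810 for visits over weeks 14–18, 0.779 over weeks 12–32, and 0.729 with every visit at week 32. The planned percentage is 10.5%, 10.9% and 11.5%. The small rise comes from longer exposure to loss.

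**5. Limits of Kaplan-Meier.** Under the middle pattern of step 3, if 25% of treated eyes leave and are treated unseen, Kaplan-Meier reads 7.6% and the planned percentage 9.4% against a true 10.0%. Also, if visits are spread evenly over weeks 14–18, about half the eyes have been censored by week 16.

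**The case against.** The SAP already states the denominator, admits its direction and rules out a between-group comparison. No P value or decision depends on this percentage, and the admitted bias is well inside sampling error. This stands, and it keeps the point minor.

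A reader might infer from the window that the reported figure could lie anywhere from 7.6% to 19.0%. The documents do not support that. Reaching 19.0% needs a constant rate of treatment start and every primary visit at week 32, whereas the target window is 16 weeks plus or minus 2. Under Protocol 3.6, treatment follows a vision loss measured at a visit, in one case confirmed at two visits, or else chair approval. No scheduled visit lies between week 12 and the primary visit. Late visits then add risk only through unscheduled visits, and step 4 may be nearer the truth than step 3.

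A reader might also infer that Kaplan-Meier removes both problems outright. It does so only if censoring is unrelated to the risk of treatment, and step 5 shows that it can do worse than the planned percentage when treated eyes disappear from view. Finally, a week-16 reading leaves out treatment started between week 16 and a later primary visit. That is why it belongs beside the crude figure and not in its place.

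**Conclusion.** The point holds as a low-cost improvement in reporting. The denominator bias is real and disclosed, about 0.3 to 0.9 points for an assumed risk of 5% to 20% with 10% random loss. Mixed follow-up may add roughly 2 to 4 points at an assumed 10% risk, provided many visits are late and risk continues to accrue after week 16; otherwise it adds little. All sizes rest on assumed rates, loss and visit timing.

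It would go too far to say that this percentage distorts the design of the pivotal trial. Protocol 7.19 and SAP 6.0 name the visual acuity standard deviation and compliance as design inputs, not this percentage. The primary analysis and the sample size are unaffected.

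**What to change.** Keep the crude count and percentage. In SAP 2.2, add by arm the Kaplan-Meier cumulative proportion starting alternative treatment by a fixed time, for example week 16, with 95% CI and numbers at risk. Include all randomized eyes, and censor untreated eyes at the primary outcome visit or last contact, whichever comes first.

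State beside it that the estimate assumes censoring unrelated to treatment risk and does not recover treatment given elsewhere after dropout.

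Reconcile the definition for treatment on the day of the primary visit: the Protocol Summary counts treatment *by* that visit, while SAP 2.2 and Protocol 7.8 count treatment *before* it.

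The cost is one descriptive estimate. The date of first alternative treatment is already needed for the last-observation rule in SAP 2.1 and the compliance denominators in SAP 2.2, and visit dates are already used in SAP 4.0.
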